Improved access to precise measurement of capillary refill time will help expand the capabilities of experienced providers who are treating patients remotely through telehealth or less experienced providers treating patients in remote locations. This is especially important in low-resource settings or regions remote from specialty centers where providers may not be as experienced in the care of children. Triaging care for conditions such as pediatric dehydration is challenging due to lack of resources, especially in developing countries. However, even in well-developed nations, access to specialized care for pediatric patients is still lacking. Pediatric specialized care in the United States is largely regionalized. Most seriously ill children present first to community hospitals where resources and expertise to treat these children may be limited. In fact, more than 90 percent of emergency department visits for children in the United States are to non-specialty facilities (11). Admission rates for large specialty pediatric hospitals are 2-4 times larger than general emergency departments suggesting that the majority of providers caring for children have limited experience in treating higher acuity pediatric conditions (12). Additionally, in the setting of rising health care costs, many parents and other non-professional caregivers are increasingly seeking health information from non-traditional sources such as mobile smartphones.

- 2.1 Preliminary Data: A pilot study is ongoing on healthy adult volunteers. This study is not yet published in a peer-reviewed journal. The study's main objective is to compare CRT measured from Cap App versus manual visual assessment under differing temperature controls. The study has enrolled 19 participants, age 20-34; 9 female, 10 male. There is some variance in skin tone. We controlled for 5 temperature conditions (30°C, 27.5°C, 25°C, 22.5°C, 20°C) utilizing an ice bath to determine variance of CRT measurement under progressively colder temperatures. The results show that Cap App measures a longer CRT with greater variance in relation to the colder temperatures. It tends to overestimate CRT for darker skin tones. Overall, CRT is longer for Cap App than for a correlated, manual CRT measurement.

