3.0 Study Endpoints/Events/Outcomes

- 3.1 Primary Endpoint/Event/Outcome: Determining the accuracy and precision of a mobile health application (Cap App) to measure CRT in an otherwise healthy pediatric patient population.
- 3.2 Secondary Endpoint(s)/Event(s)/Outcome(s): To establish normal values of CRT via Cap App for healthy children of varying age ranges, determine if subject characteristics such as skin tone, skin temperature, sex, or age affect the CRT measured via the Cap App, and determine if the CRT measured via the Cap App correlates to the manual measurement of CRT in healthy children at varying age ranges.

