5.0 Procedures Involved

5.1 Study Design: The study design will be a cross-sectional study. The observation will be to collect the CRT from a population of healthy pediatric participants. Participants who meet the inclusion criteria will have their CRT measured using both the manual measurement (to include both human and computer annotation) and mobile health application (Cap App).

Study Procedures: **Cap App CRT measurement:** Children will be placed in a seated position, and their hand resting on a table top in a resting position. The research assistant will use a smartphone with the mobile health application (Cap App) to measure the CRT. The phone will be placed on a tabletop with the front facing camera face up. The subject's index fingertip will be placed onto the camera of the smartphone with minimal pressure. The finger will then be pressed firmly against the camera for a total of 5 seconds and then released from firm pressure while still contacting the camera with instructions from the Cap App. The research assistant then presses "stop" on the Cap App device. The Cap App will then measure the amount of time it takes for blood to refill the capillary bed as evidenced by the signal return to normal of light shining on the capillary bed. This measurement will be kept blinded to the researcher and be uploaded to a secure web-based cloud server, Box, for analysis. To establish the reproducibility of the index test (or the ability of the test to be accurately replicated), the CRT will be repeated at least twice on the index fingertip with at least 15 seconds between tests, and twice on the index finger of the opposite hand, all within 30 to 60 seconds of each other.

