Manual CRT measurement: Children will be placed in a seated position with their hand raised slightly above the level of the heart on a table. A tripod will be set up for the smartphone to video record the capillary refill test by facing the table from the top. The recording will begin, and audio will not be recorded. The research assistant will compress the index finger of the participant for 5 seconds with transparent plastic and then release the pressure, after which the plastic will be removed from the field of view of the camera. The camera recording will then be stopped once the research assistant has determined the color has returned to its original color. To establish the reproducibility of the index test (or the ability of the test to be accurately replicated), the CRT will be repeated at least twice on 1 fingertip with at least 15 seconds between tests, and twice on the index finger of the opposite hand, all within 30 to 60 seconds of each other. The video, without audio, will be stored in the University of Minnesota's secure online storage platform, Box. For analysis the research study team will complete the following:

- Human annotation from manual CRT measurement: The video will be annotated blindly by a separate research team member than the one who performs the CRT manual measurement. The CRT will be measured as the

MEDICAL PROTOCOL (HRP-590)

PROTOCOL TITLE: Capillary Refill Time Measurement Utilizing Mobile Application (Cap App) in Children

VERSION DATE: 10/27/2022

amount of time required for the index finger color to return to its pre-compressed color. The measurement will be annotated by a trained human from the video recording by measuring the CRT with a stopwatch, as is the current standard.

- Computer annotation from manual CRT measurement: The same video from the manual CRT measurement will be used for the computer annotation. A research team member will manually select a section of the finger for use in the analysis and then a computer will analyze the color using signal processing. This annotation will serve as the gold standard of what is possible for human visual CRT measurement.

Individually Identifiable Health Information: Electronic data collection forms will be used to collect all relevant variables to help interpret CRT measurements in the context of the healthy patient populations. In brief, the following is the information that will be collected:

1) For healthy participants:

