15.3 Statistical Analysis: We will recruit pediatrics patients aged 1 month to 17 years who are presenting to the D2D: The Driven to Discover Research Facility at the Minnesota State Fair. Descriptive statistics will be used to summarize the data collected. For the primary outcome, we will calculate mean CRT along with 95% confidence intervals, both overall and by age group, sex, and skin tone. We will attempt to enroll a minimum of 48 patients per age group for a total of 240 patients. Initial results showed an average standard deviation of 0.663 seconds across all patients at normal hand temperature. When the sample size is 48, a two-sided 95% confidence interval for a mean will extend ± 0.188 seconds. For a total sample size of 240, a two-sided 95% confidence interval for a mean will extend ± 0.084 seconds. Human annotation of a video recording using a stopwatch will be used to measure the manual CRT measurement and we will perform computer annotation of the video recording as a gold standard. For human and computer annotations we will calculate inter-rater reliability by repeating annotations with a different observer on 10% of a random group of CRT measurements. Inter-rater reliability will be evaluated using intraclass correlation coefficients (ICCs) and Bland–Altman plots.

15.4 Data Integrity: The research assistant will obtain study eConsent and fill the data collection forms which will be embedded into the Cap App and will be password protected. The data forms, video recordings for human and computer annotation, and Cap App CRT measurement will then be uploaded to a secure web-based data storage platform, Box. The research assistant will erase the data on the smartphones every shift and will store them in a secure location at all times. The *consent forms, assent forms, and case report forms* will be electronic (UMN REDCap eConsent). No paper copies will be utilized.

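### The analysis labelled primary, mean CRT with a 95% CI, does not estimate the primary endpoint, the accuracy and precision of Cap App

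*Combined protocol and SAP*

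**What the plan says.** Section 3.1 gives the primary endpoint as "Determining the accuracy and precision of a mobile health application (Cap App) to measure CRT in an otherwise healthy pediatric patient population". Section 3.2 lists the secondary aims. These include normal values of Cap App CRT by age, the effect of child characteristics, and whether one can "determine if the CRT measured via the Cap App correlates to the manual measurement of CRT".

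Section 15.3 ties one analysis to the primary outcome: "For the primary outcome, we will calculate mean CRT along with 95% confidence intervals, both overall and by age group, sex, and skin tone". It does not say which method's CRT is averaged. It justifies the sample size by the CI half-width for a mean, ±0.188 s at n = 48 and ±0.084 s at n = 240, from an SD of 0.663 s. ICCs and Bland-Altman plots also appear in 15.3, but only for inter-rater reliability of the human and computer annotations, on a random 10% of measurements.

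Section 15.1 plans to compare Cap App with the human and computer readings within each child, and assigns the second to fourth readings to intra-rater reliability. It names no statistic for either purpose. Section 5.1 provides the data: for Cap App, "the CRT will be repeated at least twice on the index fingertip with at least 15 seconds between tests", and twice on the other hand, with a parallel scheme for the manual method. On computer annotation of the manual video, 5.1 says: "This annotation will serve as the gold standard of what is possible for human visual CRT measurement".

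Section 2.1 reports from the adult pilot: "Overall, CRT is longer for Cap App than for a correlated, manual CRT measurement".

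**The concern.** Accuracy of a measuring device is its departure from a reference. Precision is the scatter of its repeat readings on the same subject. A mean CRT with a confidence interval is neither. It contains no reference, and its width mixes true variation between children with measurement error and shrinks as children are added, whatever the quality of the app. Mean CRT by age, sex and skin tone suits the normal-values aim in 3.2.

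Section 15.2 describes the goal as the precision of the app's CRT, and 15.3 then offers the CI width of a mean. A reader could take ±0.084 s as the error of the device.

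Followed as written, the plan would report a normal-value estimate as its primary result. Agreement with the reference, and repeatability, would rest on analyses chosen later. The correlation in 3.2 does not fill the gap, because it is blind to a constant offset and the pilot reports that Cap App reads longer. Section 12.3 also allows the study to stop once the primary endpoint is judged met, which a mean CRT cannot show.

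**Working it through.** **Inputs.** From 15.3: SD 0.663 s, n = 48 per age group, n = 240 in total, two-sided 95%. From 5.1: at least two readings per hand, both hands, both methods. The documents give no within-child SD and no SD of the paired differences, so values for these are assumptions.

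**1. The plan's own figures.** Half-width of a mean = 1.96 × SD / √n.
- n = 48: 1.96 × 0.663 / √48 = 0.188 s
- n = 240: 1.96 × 0.663 / √240 = 0.084 s

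Both reproduce.

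**2. The half-width does not identify measurement error.** Take 0.663 s as the total SD with one reading per child. Let the within-child share of variance be p (assumed), so s_w = 0.663 × √p. Repeatability coefficient = 1.96 × √2 × s_w.

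| p (assumed) | s_w (s) | Repeatability (s) | CI half-width, n = 240 (s) |
|---|---|---|---|
| 20% | 0.297 | 0.82 | 0.084 |
| 50% | 0.469 | 1.30 | 0.084 |
| 70% | 0.555 | 1.54 | 0.084 |

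Section 15.3 does not say whether 0.663 s is between people, within people or both. If it were wholly within-person, repeatability would be 1.96 × √2 × 0.663 = 1.84 s.

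A noisier app in the same children does widen the interval. With an assumed between-child SD of 0.646 s:
- within-child SD 0.148 s (assumed): total √(0.646² + 0.148²) = 0.663 s, half-width 0.084 s
- within-child SD 0.629 s (assumed): total √(0.646² + 0.629²) = 0.902 s, half-width 0.114 s

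The interval alone does not show whether the children or the app caused the change.

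**3. Neither the half-width nor the correlation sees an offset.** Let Cap App = reference + offset + noise, with reference SD 0.663 s and noise SD 0.3 s (both assumed for illustration).
- SD of Cap App = √(0.663² + 0.3²) = 0.728 s
- correlation = 0.663 / 0.728 = 0.91
- half-width at n = 240 = 1.96 × 0.728 / √240 = 0.092 s

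The offset enters none of these, so offsets of 0, 0.5 and 1.0 s give the same three values. The expected mean paired difference is 0, 0.5 and 1.0 s.

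**4. What the planned data can deliver.** With one paired difference per child and SD of differences SD_d:
- bias half-width = 1.96 × SD_d / √n = 0.283 × SD_d (n = 48) or 0.127 × SD_d (n = 240)
- half-width for each limit of agreement = 1.96 × SD_d × √(1/n + 1.96² / (2(n − 1))) = 0.487 × SD_d (n = 48) or 0.217 × SD_d (n = 240)

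| SD_d (assumed, s) | Bias, n = 48 | Bias, n = 240 | Each limit, n = 48 | Each limit, n = 240 |
|---|---|---|---|---|
| 0.3 | ±0.085 | ±0.038 | ±0.146 | ±0.065 |
| 1.0 | ±0.283 | ±0.127 | ±0.487 | ±0.217 |

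For repeatability, two readings per hand give one degree of freedom per hand: 240 × 2 = 480 overall and 48 × 2 = 96 per age group. The chi-square 95% interval for the within-hand SD is 0.941 to 1.068 times the estimate overall, and 0.876 to 1.165 times per age group.

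**The case against.** The strongest reply is that the plan already contains what is asked for. Section 15.1 puts the within-child comparison before the normal range and gives the later readings a stated use in reliability. The study is also descriptive, minimal-risk and untested by any hypothesis, so a missing label does less harm than in a trial. It is true that both analyses are intended and the data are collected. If means were reported for all three methods, average bias would also be visible. But there would be no planned CI for the paired difference and no limits of agreement. An estimation study must still estimate its stated endpoint, and the one statistic labelled primary does not.

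A second reply is that 3.1 does not define accuracy against computer annotation, that 1.1 makes both manual methods the comparison, and that 5.1 limits the gold standard to human visual measurement. This stands in part: the choice of main comparator must be made and stated. Since 15.3 itself calls computer annotation a gold standard, it is the natural choice.

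Third, the illustrative figures depend on reading 0.663 s as the total SD of single readings. Averaging four readings per child, ignoring hand effects, would give half-widths of about 0.077, 0.066 and 0.058 s at shares of 20%, 50% and 70%. The widths in step 4 assume one pair per child, so they are a guide to the mixed-model result and not a forecast of it. These points change the illustrations but leave the mismatch untouched.

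**Conclusion.** The concern holds and should be corrected before the paired results are analysed. The mismatch follows from comparing 3.1 with 15.3 and needs no assumption. The plan's ±0.188 s and ±0.084 s are arithmetically right but describe a different quantity. The size of the gap is conditional: for a total SD of 0.663 s and one reading per child, a single half-width of ±0.084 s is compatible with repeatability coefficients from 0.82 to 1.54 s over the assumed shares, and with any constant offset from the reference. The true within-child SD and SD of differences cannot be had from the documents.

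**What to change.** In 15.3, replace the primary analysis with two parts.

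1. **Accuracy.** Mean paired difference, Cap App minus computer annotation, with its 95% CI and 95% limits of agreement with CIs. Pair by hand and use a mixed model with child and hand-within-child effects. Human annotation is the secondary comparator.
2. **Precision.** Within-hand SD and repeatability coefficient (or ICC) of Cap App from the repeat readings, with between-hand variance estimated separately.

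State acceptable bias and limits of agreement before anyone sees the paired results, or say that the aim is estimation only. Move mean CRT by age, sex and skin tone to the normal-values objective, and describe ±0.188 s and ±0.084 s as the precision of that mean. Report agreement beside the correlation in 3.2. Say what the SD of 0.663 s represents.

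Add a caveat on interpretation. The methods use separate compressions and different hand positions, "their hand resting on a table top in a resting position" for Cap App and "their hand raised slightly above the level of the heart on a table" for the manual test, so paired differences include physiological variation as well as app error.

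The cost is plan wording and some extra analysis, because both methods are already repeated on both hands. The variable lists in 4.0 and 5.1 do not include side, so confirm that the hand can be recovered from the reading order. Limits of agreement within an age group of 48 will be coarse. Recruitment was set for August 25 to September 5, 2022, before the version date of 10/27/2022. The documents do not say whether collection is complete; if it is, disclose that the primary analysis was changed afterwards.

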- 2.2 Existing Literature: Capillary refill has been utilized to assess, diagnose, or monitor many medical conditions in the pediatric population, such as hypovolemic and septic shock. Dehydration is one example of hypovolemic shock. The diagnosis of

MEDICAL PROTOCOL (HRP-590)

PROTOCOL TITLE: Capillary Refill Time Measurement Utilizing Mobile Application (Cap App) in Children

VERSION DATE: 10/27/2022

pediatric dehydration is largely based on clinical findings. There have been multiple clinical dehydration scoring systems developed to assess for dehydration in pediatric patients, but none are particularly accurate at differentiating levels of severity (4). Capillary refill has been shown to be the best individual clinical predictor of acute dehydration in children (5). Previous research has shown that video recording of capillary refill time is a promising tool to diagnose dehydration in children. Video computation of capillary refill time has been shown to be more accurate at diagnosing significant dehydration in children than overall clinical assessment by trained pediatric specialists (6). Improved access to precise measurement of capillary refill time may help improve the accuracy of the level of dehydration (mild/moderate/severe) and, thereby, reduce unnecessary ED visits and IV treatments. Our aim with this study is to establish normative values of capillary refill as measured by the Cap App so that we may utilize its accuracy to improve the detection of peripheral perfusion abnormalities in conditions such as dehydration.

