15.0 Statistical Considerations

15.1 Data Analysis Plan: We plan to utilize a Biostatistical Design and Analysis Center biostatistician from the Clinical and Translational Science Institute in the statistical analysis of our data. We will compare the manual method of CRT (human annotation with a stopwatch and computer analysis) and Cap App measurement of CRT amongst each individual subject. We will then create a normal range of Cap App CRT based on

MEDICAL PROTOCOL (HRP-590)

PROTOCOL TITLE: Capillary Refill Time Measurement Utilizing Mobile Application (Cap App) in Children
VERSION DATE: 10/27/2022

age of the subject in one of five categories (1-3 months, 3-12 months, 1-5 years, 5-12 years, and 12-17 years), sex (male or female), and race (skin tone). We will include a description of the primary diagnosis, vital signs (heart rate, blood pressure, oxygen saturation), temperature (room, patient core, and skin), and second, third, and fourth measurements of CRT (used for intra-rater reliability). Missing data will be documented as noted and the record will be excluded from analysis as applicable. Minimal missing data is expected, so missing data will not be imputed.

15.2 Power Analysis: The goal of this study is to determine the precision of the capillary refill time measured via the smartphone application, so no formal power calculation was performed.

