We anticipate screening approximately 300 children for enrollment with a total enrollment goal of at least 240 participants, with aim for 48 in each of five age categories (1-3 months, 3-12 months, 1 - 5 years, 5-12 years, and 12-17). No access to the child's medical record will be required as enrolled during the D2D State Fair location.

16.5 Please describe how you will communicate with research participants during the course of this research. Check all applicable boxes

- This research involves record review only. There will be no communication with research participants.
- Communication with research participants will take place in the course of treatment, through MyChart, or other similar forms of communication used with patients receiving treatment.
- Communication with research participants will take place outside of treatment settings. If this box is selected, please describe the type of communication and how it will be received by participants. Participants will express interest in person by presenting to the D2D: The Driven to Discover Research Facility at the Minnesota State Fair.

16.6 Explain how the research team has legitimate access to patients/potential participants: The research team will be permitted to access sources of private information because all participants will be required to sign a HIPAA waiver at the time of informed consent.

16.7 Location(s) of storage, sharing and analysis of research data, including any links to research data (check all that apply).

- In the data shelter of the Information Exchange (IE)
 - Store Analyze Share
- In the Bone Marrow Transplant (BMT) database, also known as the HSCT (Hematopoietic Stem Cell Transplant) Database
 - Store Analyze Share
- In REDCap (recap.ahc.umn.edu)
 - Store Analyze Share
- In Qualtrics (qualtrics.umn.edu)
 - Store Analyze Share
- In OnCore (oncore.umn.edu)
 - Store Analyze Share

MEDICAL PROTOCOL (HRP-590)

PROTOCOL TITLE: Capillary Refill Time Measurement Utilizing Mobile Application (Cap App) in Children
VERSION DATE: 10/27/2022

In the University's Box Secure Storage (box.umn.edu)

Store

Analyze

Share

In an AHC-IS supported server. Provide folder path, location of server and IT

Store Analyze Share

In an AHC-IS supported desktop or laptop.

Provide UMN device numbers of all devices:

Store Analyze Share

Other: see mobile device below

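### Does the normal range of Cap App CRT need a pre-specified method and its own precision figures, given that the stated half-widths are for a mean?

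*Combined protocol and SAP*

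**What the plan says.** Section 15.1 states: "We will then create a normal range of Cap App CRT based on" "age of the subject in one of five categories", together with sex and race (skin tone). Section 3.2 lists this among the secondary outcomes: "To establish normal values of CRT via Cap App for healthy children of varying age ranges". Section 2.2 gives it more weight: "Our aim with this study is to establish normative values of capillary refill as measured by the Cap App".

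The analysis that is specified and sized is a different one. Section 15.2 says "The goal of this study is to determine the precision of the capillary refill time measured via the smartphone application", and gives that as the reason for having no formal power calculation. Section 15.3 says "For the primary outcome, we will calculate mean CRT along with 95% confidence intervals, both overall and by age group, sex, and skin tone". The precision statement follows from there: "When the sample size is 48, a two-sided 95% confidence interval for a mean will extend ± 0.188 seconds", with ±0.084 s for all 240 children. The target of 48 per age category is repeated in section 16.4: "with aim for 48 in each of five age categories".

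No section says which percentiles bound the range, whether they are estimated parametrically, whether age, sex and skin tone are taken singly or jointly, or whether the limits carry confidence intervals. Section 15.1 does name a biostatistician from the Clinical and Translational Science Institute for the analysis.

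**The concern.** Someone who later uses the app will compare a child's CRT with a limit, not with a group mean. The only precision figures in the plan describe the mean, so a reader could take ±0.188 s as the reliability of an age-specific normal limit when the real uncertainty is clearly larger.

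Because the method is open, the percentiles, the estimator and the grouping could also be chosen after the data are seen. Ranges built separately in each age category would rest on 48 children each, whereas one model fitted to all 240 might give tighter limits from the same data. Finally, section 15.3 attributes the SD of 0.663 s only to initial results and does not say whether it is a between-child SD. The only preliminary data described (section 2.1) come from 19 adults.

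**Working it through.** **Inputs.** SD = 0.663 s, n = 48 per age category and n = 240 in total (all section 15.3). Assumptions not in the plan: CRT is Gaussian, 0.663 s is a between-child SD, each child contributes one value, and the normal range is the central 95%, mean ± 1.96 SD.

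**1. The plan's own figures.** Half-width for a mean = 1.96 × SD / √n.
- n = 48: 1.96 × 0.663 / 6.928 = 0.188 s.
- n = 240: 1.96 × 0.663 / 15.492 = 0.084 s.

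Both are reproduced.

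**2. A Gaussian normal limit.** Half-width = 1.96 × SD × √(1/n + 1.96²/(2(n − 1))).
- n = 48: 1.96 × 0.663 × √(0.02083 + 0.04087) = 1.2995 × 0.2484 = 0.323 s.
- n = 240: 1.96 × 0.663 × √(0.00417 + 0.00804) = 1.2995 × 0.1105 = 0.144 s.

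The ratio to the half-width for a mean is 0.323/0.188 = 1.72 and 0.144/0.084 = 1.71. At n = 48, assumed SDs of 0.4 s and 1.0 s give 0.195 s and 0.487 s.

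**3. Would one pooled model do better?** Take five age categories, sex, three equal skin-tone groups (assumed) and a common SD. Residual degrees of freedom are 240 − 8 = 232. The half-width for an age category, averaged over tone, is 1.96 × 0.663 × √(1/48 + 1.96²/(2 × 232)) = 1.2995 × √(0.02083 + 0.00828) = 0.222 s. The apparent gain is 0.323 − 0.222 = 0.10 s. Three checks qualify it.

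*Unequal SDs.* If the SD is estimated within each age category, the simulated half-width is 0.320 to 0.325 s, so the gain is gone. Suppose instead that one category's SD is 1.2 times that of the other four, with root-mean-square SD 0.663 s. The common SD of those four is 0.663 × √(5/(4 + 1.44)) = 0.636 s and the larger one is 0.763 s. A common-SD limit in that category is off by 1.96 × (0.663 − 0.763) = −0.20 s, about twice the precision gained.

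*Could a check of the SD catch this?* In simulations of five groups of 48 with that pattern, Levene's test (median-centred) rejects at the 5% level about 19% of the time and Bartlett's about 24%. A rule of keeping the common SD unless a test rejects would usually keep the wrong one.

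*Averaging over skin tone.* A tone-averaged mean plus 1.96 residual SDs leaves out the spread between tones. With three equal tone groups and assumed effects of −0.3, 0 and +0.3 s, the true 97.5th percentile of the mixture is 1.384 s above the mean. The line sits at 1.299 s, which is 0.08 s too low, and 3.3% of healthy children exceed it instead of 2.5%. With effects of ±0.5 s it is 0.22 s too low and 4.7% exceed it.

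Limits for a single age-sex-tone combination avoid that last problem, but their simulated half-widths are about 0.27 s with three equal tone groups, 0.31 s with six, and 0.35 s for a tone held by 10% of children. Most or all of the gain over 0.323 s is then lost.

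**The case for a change.** The strongest case for a change is that the normal range is a named deliverable, called the aim in section 2.2, and that a secondary outcome still needs a defined estimate. Naming a biostatistician does not record a method. The protocol itself expects the grouping factors to matter: section 2.0 cites variation of normal CRT with age and sex, section 2.1 reports overestimation in darker skin, and section 10.1 plans matching by age group and skin tone. Writing down the percentiles, the estimator and an interval for each limit would need only a few lines and no extra children.

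Much of this stands. The definition is missing, no redaction explains the gap, and stating it in advance would be tidier. What does not stand is the step from missing detail to a faulty plan. Section 15.3 labels its half-widths as being for a mean and attaches the mean to the primary outcome; it never offers them as the precision of a limit. Section 15.1 does not commit to separate or crossed ranges, since basing a range on age, sex and skin tone fits a model as well as separate tables. Criticism of small crossed cells is therefore aimed at a design the plan does not state.

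The pooled model is a reasonable option but not plainly better. Section 4.0 says younger children and infants may need help with pressing and that this may affect interpretation, and section 2.1 reports that Cap App variance changes with temperature. Both are reasons to doubt a common SD.

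**Conclusion.** No change to the plan follows. No stated number or rule is wrong: ±0.188 s and ±0.084 s are correct for means and are described as such. The remaining gap is the unspecified percentiles, estimator, grouping and intervals for a secondary descriptive output, which a competent analyst would fill in the usual way, by reporting a central 95% range with intervals on its limits.

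A reader who wants the precision of such a limit should expect about ±0.32 s at n = 48 and ±0.14 s at n = 240, assuming Gaussian CRT and a between-child SD of 0.663 s. At n = 48 the figure runs from ±0.19 to ±0.49 s for SDs of 0.4 to 1.0 s, a range worth keeping in mind because the source of the SD is not stated.

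Requiring a pooled common-SD model would trade a gain of about 0.10 s in half-width against a possible error of about 0.20 s in an age category whose SD is 1.2 times the others, an error that a variance test at these sizes would usually miss. The ±0.22 s figure should not be quoted as the precision of a normal limit, because it assumes equal SDs across ages and, being averaged over tone, describes the limit only if skin tone has no effect.
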